7.4 RANDOMISATION

Eligible patients will be randomised in equal ratio to Iclepertin 10mg arm and the placebo arm. The randomisation will be implemented in blocks to achieve balanced allocation to each treatment arm. In addition, randomisation will be stratified by the screening MCCB overall composite T-score (two strata: $<30, \ge 30$) with the cut-off values based on the characteristics of the MCCB overall composite T-score from historical data (R19-3841).

Page 86 of 112

Proprietary confidential information © 2023 Boehringer Ingelheim International GmbH or one or more of its affiliated companies

The randomization will be conducted via IRT. BI will arrange for the randomization and the packaging and labelling of trial medication. The randomization list will be generated using a validated system, which involves a pseudorandom number generator so that the resulting treatment will be both reproducible and nonpredictable. The block size will be documented in the CTR. Access to the codes will be controlled and documented.

7.5 DETERMINATION OF SAMPLE SIZE

Results from a phase II proof of clinical concept and dose ranging trial (1346-0009, c31477880) show the largest mean improvement of Iclepertin vs. placebo in change from baseline to Week 12 in MCCB overall composite T-score is 2 points with the estimated standard deviation of approximately 5.8 at Week 12 (the estimated standardized effect size is about 0.35), and the largest mean improvement of Iclepertin vs. placebo in change from baseline to Week 12 in SCoRS interviewer total score is 1 point with the estimated standard deviation of approximately 5.5 at Week 12 (the estimated standardized effect size is about 0.2). For this phase III trial with a treatment duration of 26 weeks and considering a treatment effect under the proposed primary estimand framework (i.e. definition of intercurrent events and the corresponding handling strategies), we assume a standardized effect size of 0.35 in the sample size calculation for the primary and the two key secondary efficacy endpoints and also assess the power of the proposed sample size under different assumptions of the standardized effect sizes for the key secondary efficacy endpoints.

The method of the two-sample t-test with equal variances and equal n's using the software nQuery + nTerim 4.0 was used to calculate the sample size based on each of the primary and the key secondary efficacy endpoints individually. An effective sample size of 220 patients per arm, 440 patients in total, will detect a standardized effect size of 0.35 in the primary efficacy endpoint, or in any of the two key secondary efficacy endpoints individually, with 95% power under one-sided type I error rate of 0.025. With 220 patients per arm and one-sided type I error rate of 0.025, a standardized effect size of 0.31, 0.286, 0.268, and 0.25 can be detected for each of the primary and the two key secondary efficacy endpoints individually with 90%, 85%, 80%, and 75% power respectively.

As a complex gatekeeping procedure is used for the hypothesis tests in this phase III trial and the controlled one-sided type I error rate for each hypothesis test depends on the result of other endpoints, it is very complicated, if not impossible, to derive the mathematical formula for the power of each efficacy endpoints considered in the gatekeeping procedure. As a result, we conducted simulations to approximate the power for each efficacy endpoint (i.e. the probability of rejecting each null hypothesis) using the gatekeeping procedure under five different scenarios of the standardized effect sizes for each efficacy endpoint with the truncation parameter γ ranging from 0.2 to 0.9, 220 evaluable patients per arm, one-sided family-wide type I error rate of 0.025, and 0.2 correlation among efficacy endpoints. We also approximate the probability of rejecting $H_{0,1}$ and one or both of $H_{0,2}$ and $H_{0,3}$ under the same five scenarios.

Simulation results as presented in Table 7.5: 1 show that with 220 evaluable patients per arm, there is at least 95% power to detect an effect size of 0.35 in MCCB overall composite T-score, regardless of the effect sizes in SCoRS interviewer total score and the adjusted total time T-score on VRFCAT. Furthermore if the effect sizes in both key secondary efficacy

Page 87 of 112

Proprietary confidential information © 2023 Boehringer Ingelheim International GmbH or one or more of its affiliated companies

endpoints are 0.35 (Scenario #1), then with 220 evaluable patients per arm we have close to 90% power to detect such effect sizes and the probability of rejecting $H_{0,1}$ and one or both of $H_{0,2}$ and $H_{0,3}$ is close to 95%. If only one of the two key secondary efficacy endpoints has an effect size of 0.35 (Scenario #2), then with 220 evaluable patients per arm we have close to 90% power to detect such an effect size and the probability of rejecting $H_{0,1}$ and one or both of $H_{0,2}$ and $H_{0,3}$ is 88.9%. If one of the two key secondary efficacy endpoints has an effect size of 0.3 but not the other key secondary efficacy endpoint (Scenario #3), then with 220 evaluable patients per arm we have 78.6% power to detect such an effect size and the probability of rejecting $H_{0,1}$ and one or both of $H_{0,2}$ and $H_{0,3}$ is 79.6%. The simulation results also show that the truncation parameter γ ranging from 0.2 to 0.9 does not impact the marginal powers for the primary and the two key secondary efficacy endpoints much. Hence we choose $\gamma = 0.2$ as this gives the desired probabilities of success for the primary endpoint (>90%) and for the key secondary efficacy endpoints (about 80%), as well as larger probabilities of success for the two secondary efficacy endpoints under Scenarios #1, #2, #3 and #4 as compared with a larger γ value such as 0.8.

In summary with 220 evaluable patients per arm, simulation results show satisfactory operational characteristics of the proposed gatekeeping procedure under Scenarios #1, #2 and #3 which are considered plausible for this phase III trial.

Table 7.5: 1 Probability of success for each endpoint under different scenarios of effect sizes from simulations

Efficacy Endpoints	Primary: MCCB Overall	Key Secondary: SCoRS total score	Key Secondary: VRFCAT	Secondary: Tower of London	Secondary: PRECIS	Primary and Key Secondary: reject H _{1,0} and (H _{2,0} and/or H _{3,0})
Scenario #1 (assumed standardized effect sizes)	0.35	0.35	0.35	0.275	0.275	
Probability of rejecting null from 1000000 simulations	95.6%	89.3%	89.3%	75.2%	75.2%	94.6%
Efficacy Endpoints	Primary: MCCB Overall	Key Secondary: SCoRS total score	Key Secondary: VRFCAT	Secondary: Tower of London	Secondary: PRECIS	Primary and Key Secondary: reject H _{1,0} and (H _{2,0} and/or H _{3,0})

c33087946-03 Clinical Trial Protocol

Page 88 of 112

Proprietary confidential information © 2023 Boehringer Ingelheim International GmbH or one or more of its affiliated companies

Table 7.5: 1 Probability of success for each endpoint under different scenarios of effect sizes from simulations (con't)

-			T	1	1	,
Scenario #2 (assumed standardized effect sizes)	0.35	0.1	0.35	0.2	0.275	
Probability of rejecting null from 1000000 simulations	95.6%	12.8%	88.6%	37.5%	60.9%	88.9%
Scenario #3 (assumed standardized effect sizes)	0.35	0.1	0.3	0.2	0.2	
Probability of rejecting null from 1000000 simulations	95.6%	12.6%	78.6%	32.4%	32.4%	79.6%
Scenario #4 (assumed standardized effect sizes)	0.35	0.1	0.25	0.2	0.275	
Probability of rejecting null from 1000000 simulations	95.6%	12.5%	62.7%	30.0%	46.7%	65.2%
Scenario #5 (assumed standardized effect sizes)	0.35	0	0	0.2	0.275	
Probability of rejecting null from 1000000 simulations	95.6%	1.3%	1.3%	1.5%	2.0%	2.4%

With 220 evaluable patients per arm, one-sided family-wise type I error=0.025, correlation between the endpoints is 0.2, truncation parameter $\gamma = 0.2$, and the gatekeeping procedure as shown in Figure 7.1: 1.

Based on the proportions of early treatment termination, patients with missing data and missing data patterns as observed in our phase II trial 1346-0009 and anticipating higher proportions of early treatment termination based on previous literatures in long-term antipsychotic trials and more patients with missing data in our phase III trial due to longer

Page 89 of 112

Proprietary confidential information © 2023 Boehringer Ingelheim International GmbH or one or more of its affiliated companies

treatment duration, we project 30% to 40% patients will prematurely terminate treatment in our phase III trial. Since BI will take every measure to collect all data at the planned visits from early dropout patients, we anticipate 25% to 50% of these early dropouts will have efficacy outcomes collected after treatment termination and can be used in the analysis. Based on these estimations, we will apply 25% correction for missing data in the sample size calculation for this phase III trial. This gives a total number of 586 randomized patients for the phase III trial, with 293 randomized patients in each treatment arm.

c33087946-03

Clinical Trial Protocol

Page 90 of 112

Proprietary confidential information © 2023 Boehringer Ingelheim International GmbH or one or more of its affiliated companies

8. INFORMED CONSENT, TRIAL RECORDS, DATA PROTECTION, PUBLICATION POLICY, AND ADMINISTRATIVE STRUCTURE

The trial will be carried out in compliance with the protocol, the ethical principles laid down in the Declaration of Helsinki, in accordance with the ICH Harmonized Guideline for GCP, relevant BI Standard Operating Procedures (SOPs), the EU directive 2001/20/EC / EU regulation 536/2014 the Japanese GCP regulations (Ministry of Health and Welfare Ordinance No. 28, March 27, 1997) and other relevant regulations. Investigators and site staff must adhere to these principles. Deviation from the protocol, the principles of ICH GCP or applicable regulations as will be treated as "protocol deviation".

Standard medical care (prophylactic, diagnostic and therapeutic procedures) remains the responsibility of the treating physician of the patient.

The investigator will inform the sponsor immediately of any urgent safety measures taken to protect the trial patients against any immediate hazard, as well as of any serious breaches of the protocol or of ICH GCP.

The Boehringer Ingelheim transparency and publication policy can be found on the following web page: trials.boehringer-ingelheim.com. The rights of the investigator and of the sponsor with regard to publication of the results of this trial are described in the investigator contract. As a rule, no trial results should be published prior to finalisation of the Clinical Trial Report.

The certificate of insurance cover is made available to the investigator and the patients, and is stored in the ISF.

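### Does the roughly 80% success probability quoted for the key secondary endpoints misstate the power for SCoRS?

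*Protocol*

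**What the plan says.** Protocol section 7.5 reports the phase II evidence: "the largest mean improvement of Iclepertin vs. placebo in change from baseline to Week 12 in SCoRS interviewer total score is 1 point", with a standard deviation of about 5.5, which it describes as a standardized effect of about 0.2. For the new trial, citing the 26-week duration and the estimand, it states that "we assume a standardized effect size of 0.35 in the sample size calculation for the primary and the two key secondary efficacy endpoints". The evaluable number is given as "An effective sample size of 220 patients per arm, 440 patients in total", which detects 0.35 on any one of these endpoints "with 95% power under one-sided type I error rate of 0.025".

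Table 7.5:1 then gives simulated rejection probabilities under the full gatekeeping procedure for five sets of effects. SCoRS is assigned 0.35, 0.1, 0.1, 0.1 and 0; VRFCAT is assigned 0.35, 0.35, 0.3, 0.25 and 0. The text states that varying the truncation parameter from 0.2 to 0.9 "does not impact the marginal powers for the primary and the two key secondary efficacy endpoints much". It chooses 0.2 for two reasons: it gives "the desired probabilities of success for the primary endpoint (>90%) and for the key secondary efficacy endpoints (about 80" per cent), and it raises the success probabilities for Tower of London and PRECIS compared with a larger value. Scenarios #1 to #3 are the ones called plausible.

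**The concern.** The 80% figure is attached to the key secondary endpoints in the plural, without a definition or a scenario. Read as the power of each endpoint, it conflicts with the table: SCoRS is 12.8%, 12.6% and 12.5% in Scenarios #2 to #4, and VRFCAT is 62.7% in Scenario #4. The phase II SCoRS effect is 1/5.5 = 0.18, yet the scenarios jump from 0.1 to 0.35, the latter almost double the observed value. The truncation parameter was therefore chosen without tabulating the case closest to the SCoRS data.

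SCoRS is one of only two measures of the key secondary objective, daily functioning. If the sponsor believed it had 80% power for SCoRS when it had half that, a non-significant SCoRS result would be more likely than the planning text suggests, and a different truncation parameter might have been preferred.

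**Working it through.** **Inputs** (Protocol sections 7.1, 7.4 and 7.5): one-sided alpha 0.025; 220 evaluable per arm; 1:1 allocation; correlation 0.2 between endpoints; truncation parameter γ = 0.2.

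**Rules.** The primary is tested at 0.025. Both key secondaries are rejected if both p-values are below 0.025 × (1 + 0.2)/2 = 0.015. Otherwise the smaller is tested at 0.025/2 = 0.0125. The third family receives 0.025 if both are rejected, or 0.025 × (1 − 0.2)/2 = 0.010 if one is, and uses Hochberg.

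**Method.** 1,000,000 draws of five correlated normal statistics with mean d × √(220/2) = 10.49 d.

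**Individual power reproduces.** For effects 0.35, 0.31, 0.286, 0.268 and 0.25: 95.6, 90.2, 85.1, 80.3 and 74.6%, against the stated 95, 90, 85, 80 and 75%.

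**Table 7.5:1 reproduces** (stated / recomputed, %):

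| Scenario | SCoRS effect | VRFCAT effect | SCoRS | VRFCAT | Primary plus at least one key secondary |
|---|---|---|---|---|---|
| #1 | 0.35 | 0.35 | 89.3 / 89.5 | 89.3 / 89.5 | 94.6 / 94.7 |
| #2 | 0.1 | 0.35 | 12.8 / 12.8 | 88.6 / 88.8 | 88.9 / 89.1 |
| #3 | 0.1 | 0.3 | 12.6 / 12.7 | 78.6 / 79.0 | 79.6 / 80.0 |
| #4 | 0.1 | 0.25 | 12.5 / 12.5 | 62.7 / 63.1 | 65.2 / 65.5 |
| #5 | 0 | 0 | 1.3 / 1.3 | 1.3 / 1.2 | 2.4 / 2.4 |

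In Scenarios #1 to #3 the endpoint that is given an effect has 89.3, 88.6 and 78.6%, and the joint criterion has 94.6, 88.9 and 79.6%. Both sets fit about 80% or better.

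**The untabulated case**, primary effect 0.35 and γ = 0.2:

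| SCoRS effect | VRFCAT effect | SCoRS power | At least one key secondary |
|---|---|---|---|
| 0.182 | 0.182 | 37.1% | 55.8% |
| 0.182 | 0.30 | 38.2% | 83.4% |
| 0.182 | 0.35 | 38.4% | 90.4% |
| 0.20 | 0.20 | 44.4% | 64.0% |
| 0.20 | 0.30 | 45.4% | 84.6% |
| 0.20 | 0.35 | 45.7% | 90.9% |

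Letting VRFCAT fall to 0 lowers SCoRS power only to 36.0% (effect 0.182) or 43.1% (effect 0.20). With SCoRS at 0.20 and VRFCAT at 0.1 or 0.35, a correlation of 0 or 0.5 in place of 0.2 moves SCoRS power by about 1 point. SCoRS reaches about 80% at an effect near 0.30 (79.0 to 80.4% for VRFCAT 0.1 to 0.35).

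**The truncation parameter.** Moving γ from 0.2 to 0.9 in the five simulated scenarios changes SCoRS from 89.5 to 91.3, 12.8 to 17.1, 12.7 to 16.8, 12.5 to 16.1 and 1.3 to 1.3%. VRFCAT changes by at most 1.8 points. With SCoRS at 0.20 and VRFCAT at 0.35, SCoRS rises from 45.7 to 52.6%, but Tower of London (effect 0.2) falls from 43.2 to 35.9% and PRECIS (effect 0.275) from 66.0 to 56.0%. With both key secondaries at 0.20 the SCoRS gain is 48.6 − 44.4 = 4.2 points; with VRFCAT at 0.1 it is 44.8 − 43.4 = 1.4 points.

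**The case for a change.** The strongest case for the concern is that section 7.5 itself equates power with the chance of rejecting each null hypothesis. On that definition SCoRS misses 80% in two of the three scenarios called plausible. For MCCB the design effect equals the phase II estimate, whereas for SCoRS it is nearly twice the estimate. Longer treatment and the estimand are mentioned, but nothing quantifies a rise from about 0.2 to 0.35. The list of individual powers stops at 0.25. At the phase II effect, SCoRS is more likely to fail than to succeed.

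The arithmetic behind this stands, and so does the remark that the 80% is undefined. Three parts do not carry. First, the SCoRS values near 13% come from an effect set at 0.1, about half the phase II value. The text says openly that Scenarios #2 and #3 have only one effective key secondary, so low power there is the scenario's premise. Second, the reference to Scenarios #1 to #4 is most naturally part of the comparison of truncation parameters for Tower of London and PRECIS; the claim of satisfactory performance covers only #1 to #3, so Scenario #4 does not contradict it. Third, the remark on the truncation parameter describes the simulated scenarios, where the largest shift is about 4 points. The 6 to 7 point gain arises only in an added case with a strong VRFCAT effect, and it is paid for by the third family.

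**Conclusion.** No change is needed. Table 7.5:1, the individual powers and the primary power of 95.6% are right for the stated inputs. The 80% statement is true, in Scenarios #1 to #3, of the key secondary endpoint with an effect of 0.30 to 0.35 (78.6 to 89.3%) and of the primary plus at least one key secondary (79.6 to 94.6%). It is not true of each key secondary endpoint separately, and the table shows that plainly.

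What remains is loose wording and one untabulated effect size. If the true SCoRS effect is 0.18 to 0.20, SCoRS power is about 36 to 46%. At least one key secondary then succeeds in about 83 to 91% of trials if VRFCAT is 0.30 to 0.35, and in about 56 to 64% if VRFCAT is as weak as SCoRS. These figures assume 220 evaluable per arm, a primary effect of 0.35, correlation 0.2 and normal test statistics.

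A reader can see the direction from the protocol itself, which reports the phase II effect of about 0.2 and only 75% individual power at 0.25. Adding the scenario would inform expectations for SCoRS. The sample size, testing order, alpha and analysis would all stay as they are, and the choice of 0.2 for the truncation parameter remains a fair trade between the second and third families.

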8.1 TRIAL APPROVAL, PATIENT INFORMATION, INFORMED CONSENT

This trial will be initiated only after all required legal documentation has been reviewed and approved by the respective IRB / Independent EC (IEC and CA according to national and international regulations. The same applies for the implementation of changes introduced by amendments.

Prior to patient participation in the trial, written informed consent must be obtained from each patient (or the patient's legally accepted representative) according to ICH-GCP and to the regulatory and legal requirements of the participating country. Each signature must be personally dated by each signatory and the informed consent and any additional patient-information form retained by the investigator as part of the trial records. A signed copy of the informed consent and any additional patient information must be given to each patient or the patient's legally accepted representative."

The investigator or delegate must give a full explanation to trial patients and study partner/caregiver based on the patient information form. A language understandable to the patient and study partner/caregiver should be chosen, technical terms and expressions avoided, if possible.

The patient and study partner/caregiver must be given sufficient time to consider participation in the trial. The investigator or delegate obtains written consent of the patient's and study partner's / caregiver's own free will with the informed consent form after confirming that the

Page 91 of 112

Proprietary confidential information © 2023 Boehringer Ingelheim International GmbH or one or more of its affiliated companies

patient and the study partner / caregiver understands the contents. The investigator or delegate must sign (or place a seal on) and date the informed consent form. If a trial collaborator has given a supplementary explanation, the trial collaborator also signs (or places a seal on) and dates the informed consent.

Re-consenting may become necessary when new relevant information becomes available and should be conducted according to the sponsor's instructions and in accordance with all applicable local regulations.

The consent and re-consenting process should be properly documented in the source documentation.

8.2 DATA QUALITY ASSURANCE

A risk-based approach is used for trial quality management. It is initiated by the assessment of critical data and processes for trial patient protection and reliability of the results as well as identification and assessment of associated risks. An Integrated Quality and Risk Management Plan documents the rationale and strategies for risk management during trial conduct including monitoring approaches, vendor management and other processes focusing on areas of greatest risk.

Continuous risk review and assessment may lead to adjustments in trial conduct, trial design or monitoring approaches.

A quality assurance audit/inspection of this trial may be conducted by the sponsor, sponsor's designees, or by IRB / IEC or by regulatory authorities. The quality assurance auditor will have access to all medical records, the investigator's trial-related files and correspondence, and the informed consent documentation of this clinical trial.

8.3 RECORDS

eCRFs for individual patients will be provided by the sponsor. See section 4.1.5.2 for rules about emergency code breaks. For drug accountability, refer to section 4.1.8.

8.3.1 Source documents

In accordance with regulatory requirements, the investigator should prepare and maintain adequate and accurate source documents and trial records that include all observations and other data pertinent to the investigation on each trial patient. Source data as well as reported data should follow the "ALCOA principles" and be attributable, legible, contemporaneous, original and accurate. Changes to the data should be traceable (audit trail).

Data reported on the eCRF must be consistent with the source data or the discrepancies must be explained.

The current medical history of the patient may not be sufficient to confirm eligibility for the trial and the investigator may need to request previous medical histories and evidence of any diagnostic tests. In this case, the investigator must make at least one documented attempt to retrieve previous medical records. If this fails, a verbal history from the patient, documented in their medical records, would be acceptable.

Page 92 of 112

Proprietary confidential information © 2023 Boehringer Ingelheim International GmbH or one or more of its affiliated companies

Copies of source documents necessary for neurocognitive assessments (e.g. MCCB) will be provided to VeraSci. Before sending or uploading those copies, the investigator must ensure that all patient identifiers (e.g. patient's name, initials, address, phone number, social security number) have properly been removed or redacted from any copy of the patients' source documents.

If the patient is not compliant with the protocol, any corrective action e.g. re-training must be documented in the patient file.

For the eCRF, data must be derived from source documents, for example:

- Patient identification: gender, year of birth (in accordance with local laws and regulations)
- Patient participation in the trial (substance, trial number, patient number, date patient was informed)
- Dates of patient's visits, including dispensing of trial medication
- Medical history (including trial indication and concomitant diseases, if applicable)
- Medication history
- AEs and outcome events (onset date (mandatory), and end date (if available))
- SAEs (onset date (mandatory), and end date (if available))
- Concomitant therapy (start date, changes)
- Originals or copies of laboratory results and other imaging or testing results, with proper documented medical evaluation (in validated electronic format, if available)
- Completion of patient's participation in the trial (end date; in case of premature discontinuation document the reason for it).
- Prior to allocation of a patient to a treatment into a clinical trial, there must be documented evidence in the source data (e.g. medical records) that the trial participant meets all inclusion criteria and does not meet any exclusion criteria. The absence of records (either medical records, verbal documented feedback of the patient or testing conducted specific for a protocol) to support inclusion/exclusion criteria does not make the patient eligible for the clinical trial.

